Chronic dacryocystitis is a common ophthalmic disease, mostly caused by nasolacrimal duct obstruction or stenosis. Tears and secretions cannot flow into the nasal cavity through the nasolacrimal duct and remain in the lacrimal sac, resulting in bacterial infection. If not treated, it can not only affect the patient's daily life, but also threaten the patient's eye health. The accumulation of pus in the lacrimal sac is a potential source of intraocular infection, which can easily lead to endophthalmitis during intraocular surgery or ocular trauma. At present, there are many measures to treat chronic dacryocystitis, the treatment principle is to dredge or re-establish the nasal drainage channel, eliminate obstruction, and inhibit infection. At present, the main treatment methods are external dacryocystorhinostomy, nasolacrimal duct intubation, lacrimal passage laser plasty and endoscopic dacryocystorhinostomy. After evolution and improvement, the operation success rate has increased to more than 90%, but there are still shortcomings such as facial skin scar, surgical trauma, damage to the "tear pump" function, and inability to treat nasal diseases at the same time. Nasolacrimal duct intubation and lacrimal passage laser plasty have the advantages of simple operation, time-saving, easy tolerance and repeatable operation. However, since they are not operated under direct vision, they are easy to form false passages, and easy to cause adhesion and scar formation between the lacrimal passage mucous membranes. The long-term efficacy is still controversial.

With the development of nasal endoscopy technology and the improvement of patients' requirements for facial aesthetics, dacryocystorhinostomy under nasal endoscopy has gradually become the main surgical method for the treatment of chronic dacryocystitis. Compared with traditional external dacryocystorhinostomy, dacryocystorhinostomy under nasal endoscope has the advantages of "tear pump" function without damage to inner canthus ligament and deep branch of orbicularis oculi muscle. It also causes no facial scar left, and can simultaneously treat the nasal complications. The operation is under high-definition magnification endoscopic vision, so that it's also a fine, simple and minimally invasive surgery. With the widespread promotion of its clinical application, it has gradually been found that the granulation or scar formation at the anastomosis after endoscopic dacryocystorhinostomy is the main reason for the failure of the operation. **How to achieve the ideal fit between the lacrimal sac flap and the nasal mucoperiosteal flap and avoid the proliferation of granulation and cicatricial adhesion is very important for the success of**

the operation. In order to improve the success rate of operation, many explorations have been made, such as suture between lacrimal sac flap and nasal mucoperiosteal flap during operation. In order to maintain the patency of the anastomosis, artificial lacrimal duct, mitomycin C and lacrimal duct dilator stent have all been applied to the anastomosis, but they all have certain disadvantages. For example, artificial lacrimal duct and dilator stent are easy to fall off and become blocked again, and need to be removed by a second operation, which is often accompanied by bleeding and can affect wound healing. Mitomycin C has certain toxic and side effects. Though it can reduce scar hyperplasia, it can also delay anastomotic wound healing and epithelialization.

In recent years, with the wide application of new technologies and new materials, the medical community and the medical polymer material community have reached a consensus that hydrogels will become a powerful tool to solve the problem of clinical wound repair and tissue flap adhesion. Hydrogel has the most similar structure and mechanical properties of human soft tissue, which can provide a good self-healing environment. Secondly, hydrogel can form an effective physical barrier, which can quickly stop bleeding, close the wound, and effectively reduce the incidence of adhesion and infection. More importantly, hydrogel has the function of drug carrier and cell scaffold, which can carry drugs, cytokines and even stem cells. These can effectively promote wound repair and healing. Therefore, the conversion of hydrogel materials into clinical products is one of the most important goals in this field. Similar to the photosensitive dental repair technology, photosensitive hydrogels can achieve *in situ* modeling of irregular wounds with excellent controllability. A single component is particularly easy to clinical operation, which is an important development direction of hydrogels medical materials. However, the current technology has an important defect due to its inability to adhere firmly to and integrate with wet tissues.

Photosensitive hydrogel products will realize the innovation of hydrophilic polymer *in situ* crosslinking forming on the wound surface. It can be adapted to any irregular wound, and the "photocoupling reaction" technology can achieve seamless integration and strong adhesion of hydrogel material and wound. Therefore, the photosensitive hydrogel products have the following advantages: (1) Excellent adhesion ability, which can realize the close adhesion and hemostasis of irregularly shaped tissue wounds, reduce wound exposure, reduce infection risk, and take into account the analgesic function; (2) The hydrogel is used as the skeleton of biological macromolecules, and the crosslinking process is mild and controllable, with excellent biosafety and

biodegradability; (3) The hydrogel is soft and elastic, with a high degree of mechanical strength consistent with human soft tissue.

The photosensitive hydrogel uses the natural human component, hyaluronic acid, as the biological macromolecule skeleton. After packaging, it has undergone strict medical grade sterilization treatment, which meets the national GB/T 16886 standard. It is non-toxic to the human body, has no allergy and rejection reaction, and ensures the biosafety to the maximum extent (see the attachment for details). Approved by the Ethics Committee of Shanghai Hospital Affiliated to Naval Medical University (see attachment for a copy of the ethics approval), clinical trials of suture-free skin trauma and chronic wound repair of more than 200 cases (including children) have been completed in its burn department since 2018, and no adverse reactions have been reported. At the same time, Yueyang Hospital of Integrated Chinese and Western Medicine affiliated to Shanghai University of Traditional Chinese Medicine, the Second Affiliated Hospital of Wenzhou Medical University and Ningbo Huami Hospital of University of Chinese Academy of Sciences respectively conducted clinical application research on postoperative wound treatment using the hydrogel, including hepatointeropathy, prevention and treatment of pediatric prepuce adhesion, and treatment of skin donor area wounds (copy of the ethical approval letter is attached).

Therefore, based on the clinical application value of photosensitive hydrogel, this study applied it to the suture-free adhesion of lacrimal cyst mucosal flap and nasal mucosal flap in endoscopic dacryocystorhinostomy. In order to achieve wound closure and promote wound healing, it can prevent postoperative anastomotic adhesion and granulation, replace the need for suture of mucosal flap, and greatly shorten the operation time.

2、Research purpose

To study the effect of photosensitive hydrogel used for suture-free anastomosis of lacrimal cyst and nasal mucoperiosteal flap in endoscopic nasal dacryocystorhinostomy. To evaluate its ability to promote wound healing, forming a good anastomosis, preventing postoperative anastomosis and shortening operation time.

3、Type of study design, randomized grouping method and blind level

This study was a single-blind, prospective, parallel controlled, single-center clinical study, randomized by random number method.

4、Subject inclusion criteria, exclusion criteria, discontinuation criteria

4.1 Study case inclusion criteria

- 1) Voluntarily participate in this clinical study and sign the informed consent;
- 2) Gender is not limited, age 18-75 years old;
- 3) The patient had symptoms and signs of chronic dacryocystitis, and the results of lacrimal passage irrigation suggested that the lower rush and return or upper rush and lower return, accompanied by mucous or purulent discharge reflux;
- 4) CT dacryocystography suggests nasolacrimal duct obstruction without lacrimal canaliculi and/or duct obstruction.

4.2 Exclusion criteria

- 1) Age < 18 or > 75 years old;
- 2) Previous history of dacryocystorhinostomy;
- 3) Abnormal coagulation function;
- 4) Tumors of lacrimal passage, especially in patients with papilloma or malignant tumors;
- 5) in the acute dacryocystitis attack stage;
- 6) obvious scar constitution;
- 7) Complicated with serious nasal diseases, such as severe allergic rhinitis, chronic rhinosinusitis and nasal polyps, acute suppurative rhinosinusitis, severe atrophic rhinitis, and severe deviation of nasal septum;
- 8) Have serious heart, liver, kidney, lung and other basic diseases, cannot tolerate general anesthesia;
- 9) Distance from the hospital, postoperative review is not convenient;
- 10) Participated in other clinical trials within the last 3 months;
- 11) Any medical history that the investigator determines may interfere with the test results or increase the patient's risk.

4.3 Termination and exit criteria

- (1) Observation of the influence of other diseases during treatment;
- (2) Poor compliance, cannot strictly implement the program, failed to treat according to regulations;
- (3) Drugs that may affect the observation of the study need to be used in combination during the trial;

- (4) Lost follow-up;
- (5) The research object asks to quit;
- (6) Serious adverse events;
- (7) The researcher considers it necessary for the subjects to terminate this study.

5、Research method

5.1 Subject selection: This was a single-center, randomized, parallel controlled clinical trial to evaluate the efficacy and safety of endoscopic dacryocystorhinostomy using suture and photosensitive hydrogel. The study plan included 20 subjects, all of whom were randomly assigned 1:1 to either the suture group or the photosensitive hydrogel group.

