5.3 Endoscopic dacryocystorhinostomy

The patient was placed in supine position under general anesthesia, and was routinely disinfected and laid down. Epinephrine injection 1ml was mixed with 2% lidocaine injection 20ml. The nasal mucosa was contracted with cotton pads impregnated with the mixture, and the nasal submucosal infiltration was performed on the anterior uncinate process in the anterior axillary of the middle turbinate. Under the direct vision of 0-degree ultra-wide angle endoscope, a nasal mucosa incision of about 1.0cm×0.8cm was made in the anterior axillary part of the middle turbinate parallel to the uncinate process to form a nasal mucosa flap, which separated the nasal mucosa and pushed it to the rear, covered with cotton sheets for protection, exposed the bone, and visible lacrimal-maxillary suture. The bone was thined by dynamic system, and the bone was removed by bone biting forceps. A bone window about 1.0cm×1.2cm in size was formed to expose the lacrimal sac and trim the edge of the bone window to make it smooth. The probe was introduced into the lacrimal

sac through the upper lacrimal dot and lacrimal canaliculi and lifted up the inner wall of the lacrimal sac. The puncture bayonet was gently bent about 30 degrees to cut the lacrimal sac, and the lacrimal passage was rinsed to observe whether liquid flowed from the lacrimal sac incision, so as to confirm whether the lacrimal sac wall was cut. The pedicled nasal mucoperiosteal flap was pruned and covered in the surrounding bone window, respectively. The lacrimal sac mucoperiosteal flap was anastomosed with the nasal mucoperiosteal flap. The experimental group and the control group were divided into two groups for mucoperiosteal anastomosis intervention.

5.4 Research groups:

A、Trial group: 10 patients were expected to be included. The lacrimal cyst mucosal flap and nasal mucoperiosteum flap were anastomosed with photosensitive hydrogel. Appropriate amount of photosensitive hydrogel was applied on the surface of the trimmed and flat mucosal valve, which was irradiated by a light source of 395 nm for about 15 s to solidify and bond.

B、Control group: 10 patients are expected to be included. The lacrimal membrane flap and nasal mucoperiosteal flap were anastomosed by suture method, and the 6-0 absorbable thread was used to suture 2 stitches.

[figure not shown]

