5.5 Postoperative follow-up: All subjects were required to have four outpatient follow-up visits (2 weeks, 6 weeks, and 12 weeks). The following indicators should be observed at each follow-up visit:

- 1) Whether the postoperative symptoms of tears and pus disappeared;
- 2) Whether the tear duct is unobstructed;
- 3) The anastomosis was well opened and there was no granulation or scar formation under endoscope.

The main evaluation index of this study was that the opening of the anastomosis was observed by nasal endoscopy at 6 weeks. The secondary outcome measures were the remission of tearing symptoms assessed by VAS scale at 2, 6, and 12 weeks.

Safety evaluation indicators: anastomotic scar, granulation, wound infection, allergic reaction, eye slit-lamp examination and vision examination.

6、Implementation steps and test flow chart

The following table is the test flow table:

Item	pre-operation	postoperation		
		2 weeks	6 weeks	12 weeks
Cases were identified for inclusion/exclusion	√			
Sign informed consent	√			
General information	√			
Medical history and treatment history	√			
Concomitant disease	√			
Signs and symptoms	√	√	√	√
Vision	√	√	√	√
Slit-lamp examination	√	√	√	√
Lacrimal duct irrigation	√		√	√
CT Dacryocystography	√			
Nasal endoscopy	√	√	√	√
Anastomotic opening state		√	√	√

Scar condition of anastomosis		√	√	√
Granulation condition of anastomosis		√	√	√
Adverse reaction evaluation		√	√	√

7、Research risk

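### Section 4.3 lets post-operative events end study participation after the intervention is complete, and nothing secures the 6-week primary endoscopy for patients who exit

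*Protocol*

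**What the plan says.** Section 4.3 of the protocol is one undivided list of termination and exit criteria. Item (3) is "Drugs that may affect the observation of the study need to be used in combination during the trial". Item (6) reads "6) Serious adverse events". Item (7) is "The researcher considers it necessary for the subjects to terminate this study". They stand on the same footing as loss to follow-up (4) and the patient's own request (5). Items (1), the influence of other diseases, and (2), poor compliance, complete the list.

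Section 5.4 describes both interventions as single acts during surgery. The control arm receives two stitches. In the trial arm the hydrogel is applied to the flap, "which was irradiated by a light source of 395 nm for about 15 s to solidify and bond". No post-operative study treatment is described.

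Section 5.5 fixes the primary outcome: "The main evaluation index of this study was that the opening of the anastomosis was observed by nasal endoscopy at 6 weeks". It also states: "All subjects were required to have four outpatient follow-up visits". It does not say whether this still applies to someone who has exited under 4.3.

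Section 7 has adverse events treated and followed until they are normal or stable. In the case report form, the adverse event form has a No/Yes box for quitting the trial. The completion page takes a trial exit date and lists an adverse event and an investigator decision among the reasons.

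**The concern.** In a trial with continuing treatment, an exit list often mixes stopping treatment with leaving the study. Here, once the patient has been operated on, no study treatment remains to be stopped. An exit between surgery and week 6 can only remove observation, and the observation at risk is the primary one.

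The exits may also be related to outcome. The background says that "the granulation or scar formation at the anastomosis after endoscopic dacryocystorhinostomy is the main reason for the failure of the operation". Section 5.5 counts related local findings as safety outcomes: "Safety evaluation indicators: anastomotic scar, granulation, wound infection, allergic reaction". Section 7 has adverse events treated, and such treatment could involve a drug that falls under item (3). Section 8 makes hospitalisation a serious adverse event, which is item (6). Closure, scar and granulation are not exit criteria themselves, so the link is possible rather than established.

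If such patients leave before week 6 without endoscopy, the open rate is computed on a selected group. How missing outcomes are analysed can be left to a statistical analysis plan. Whether the endoscopy is done at all is a protocol matter, and no analysis recovers one that was not done.

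**Working it through.** **Does the text secure the endoscopy after an exit?**

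- 4.3, items (3), (6) and (7): can arise between surgery and week 6. Item (7) speaks of ending the study, not a treatment.
- 4.3, items (1) and (2): (1) is limited to the treatment period and (2) may partly concern the operation. They count here only where they arise after surgery.
- 5.5: requires visits of every subject, but is silent on subjects who have exited.
- Section 7: follow-up ends at resolution or stability and is not tied to week 6.
- Case report form: records exit and its reason. It has no field for a week-6 endoscopy after exit.
- 4.2, exclusion 9 (review inconvenient): limits ordinary loss to follow-up, not exits under (3), (6) or (7).

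No provision secures it.

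**Inputs.** From the protocol: 20 patients, 1:1, so 20 × 1/2 = 10 per arm (5.1, 5.4). The protocol gives no exit rate, expected open rate or dropout allowance, so all rates below are assumptions.

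**Information lost per patient.** One missing of 10 is 1/10 = 10 points of that arm's rate. The range left open for the between-arm difference is 10 × (missing in arm A + missing in arm B) points: 20 with one missing per arm, 40 with two per arm.

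**Chance of at least one missing endoscopy.** With exit risk q per patient before week 6, this is 1 − (1 − q)^20:

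- q = 2%: 33% (expected missing 0.4)
- q = 5%: 64% (expected missing 1)
- q = 10%: 88% (expected missing 2)

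**Possible shift of one arm's open rate.** Let p be the true open rate, and qO and qF the exit risks of open and failed cases. The expected observed rate is p(1 − qO) / [p(1 − qO) + (1 − p)(1 − qF)]. For example, p = 0.80, qO = 0.10, qF = 0.30 gives 0.72 / (0.72 + 0.14) = 83.7%.

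| qO | qF | p = 80%: observed (shift) | p = 90%: observed (shift) |
|---|---|---|---|
| 10% | 10% | 80.0 (0) | 90.0 (0) |
| 10% | 20% | 81.8 (+1.8) | 91.0 (+1.0) |
| 10% | 30% | 83.7 (+3.7) | 92.0 (+2.0) |
| 10% | 50% | 87.8 (+7.8) | 94.2 (+4.2) |
| 20% | 10% | 78.0 (−2.0) | 88.9 (−1.1) |

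If only one arm has an outcome-related pattern, this shift is the between-arm bias. If both arms have the same pattern and the same true rate, the expected bias is about zero. With the same pattern but true rates of 90% and 80%, the 10-point difference reads 9.2, 8.3 or 6.4 points for qF of 20%, 30% or 50% (qO = 10%).

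**Against sampling error.** At 80% open, the standard error is √(0.8 × 0.2 / 10) = 12.6 points per arm and √(2 × 0.8 × 0.2 / 10) = 17.9 points for the difference. At 90% they are 9.5 and 13.4. Every shift in the table is smaller than the matching per-arm standard error.

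**A concrete extreme.** Suppose 8 of 10 are truly open in each arm and both failures in one arm exit unseen. The comparison becomes 8/8 against 8/10, and Fisher's exact two-sided p is (45 + 28)/153 = 0.48.

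**The case against.** The strongest reply is that this is an ambiguity, not an error. Section 4.3 does not say that visits stop, and 5.5 requires visits of every subject without exception. The adverse event form has a No/Yes box, so quitting is decided event by event. Items (1) and (2) are not clearly post-operative. Getting from a failing anastomosis to a missing endoscopy takes several steps: an event, a drug judged to interfere or a serious event, an exit, and a skipped visit. Scar or granulation recorded as an adverse event would be followed to stability anyway. The window is six weeks, 4.2 screens out serious nasal and systemic disease, and the background reports more than 200 earlier cases without reported adverse reactions, although in other wounds.

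Much of this stands, and it limits the point. A reader might infer that every adverse event removes the patient; the No/Yes box contradicts that. A reader might infer that 4.3 expressly ends the visits; it does not. A reader might also infer that failures would be removed selectively in favour of the hydrogel, or that a false significant result is likely; the protocol gives no exit rates, nothing sets the direction, and the calculation does not support it.

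What does not stand is that 5.5 or Section 7 closes the gap. A list headed as exit criteria, placing these events beside loss to follow-up, is naturally read as ending participation, and the case report form records it so. Neither safeguard says that the week-6 endoscopy survives an exit.

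**Conclusion.** The point holds in limited form. Items (3), (6) and (7) of Section 4.3, and (1) and (2) where they arise after surgery, are reasons to leave a study whose intervention is already complete, and the protocol does not secure the primary endoscopy for those patients.

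The firm figure is 10 points of an arm's open rate per missing endoscopy, which follows from 10 patients per arm and would apply to any missing patient, including unavoidable losses. The frequency and direction of any bias are unknown. The shifts, from −2.0 to +7.8 points, rest entirely on assumed exit and open rates and lie below sampling error; if exits are unrelated to outcome, only precision is lost. The issue is avoidable, possibly outcome-related loss of primary data in a very small trial. It is worth correcting because the correction is cheap, not because the result is shown to be biased.

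**What to change.** In 4.3, separate leaving follow-up (withdrawal of consent, loss to follow-up) from events that are recorded while follow-up continues. State that randomised, operated patients who meet (3), (6) or (7), or (1) or (2) after surgery, have the event recorded and remain in scheduled follow-up. The 6-week endoscopy and the 12-week visit are then sought where the investigator judges it safe, unless the patient withdraws consent or is lost. Add to the visit requirement in 5.5 that it includes these patients. Clinical management of the event stays with the protocol and the investigator.

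The cost is two or three sentences, resubmitted to the ethics committee as Section 10 requires for a revised plan. The visits and endoscopies are already scheduled. The downside is a few more patients to follow and possibly a less favourable open rate.

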5.2 Preoperative evaluation

All patients underwent slit lamp, fundus and other ophthalmic examinations to exclude ophthalmic diseases, especially ocular surface diseases. The lacrimal duct was syringed to remove the stenosis or obstruction of lacrimal canaliculi or common duct. Endoscopic examination was performed to understand the nasal condition and observe whether there was obvious middle nasal passage stenosis, nasal septum deviation and nasal mucosal lesions. CT dacryocystography was performed to observe and measure the size of lacrimal sac, to understand the obstruction of nasolacrimal duct, and to determine the incision location. General examination such as chest film, electrocardiogram, biochemistry and coagulation were performed to rule out systemic lesions

